1.2. HIV risk behavior among Moscow Tajik migrants occurs in a country that has an exceedingly high and still rising HIV rate.²³ While globally new infections declined by an estimated 16% from 2010 to 2017,²⁴ in Eastern Europe and Central Asia the number of new infections grew by an estimated 30%. The Russian Federation accounts for 70% of HIV cases in this region and accounted for 75% of new HIV infections in the region in 2017.¹¹ Most HIV infections in the region are among people who inject drugs (PWID) and their sexual partners,²⁵ yet harm reduction service coverage is low. A recent study of PWID in St. Petersburg reported an HIV incidence rate of 9.3 per 100 person years.²⁶ In the Russian Federation in particular, insufficient access to sterile injecting equipment and the unavailability of opioid substitution therapy (OST) are significant roadblocks to reducing HIV infections among people who inject drugs.^{12, 27} Tajik migrants form a potential bridge for HIV to move from high-prevalence Russia to low prevalence Tajikistan, which currently has a centralized epidemic primarily among PWID. HIV prevalence among PWID in Tajikistan is estimated at 13.5% compared to 25.6% in the Russian Federation.²⁵

1.3. HIV risk behavior among Tajik labor migrants who inject drugs in Russia is alarmingly high. In our first survey of 106 Tajik migrant men who inject drugs (MWID),⁷ 105 (99%) of the sample reported using heroin in Tajikistan before relocating to Moscow; 94% reported injecting drugs at least once a week; and 83% reported having shared needles or syringes in the last 30 days. Sharing unclean "works" appears to be a normative practice. As one of our sample participants explained, "We use the same syringe and

needle every time. We share our equipment; we are one circle of friends.” Meanwhile, although knowledge that HIV can spread sexually was well-known (93%), 66% of the MWID that we sampled didn’t know it could be transmitted through unclean needles. One participant who rejects this notion remarked, ““If it is transmitted through sex, then how can there be a link between HIV and drug use? There isn’t any link.” Only 9 participants reported injecting with a non-Tajik (nearly all Russian women). Condom use was low with 74% of the MWID with regular sexual partners reporting never using them even when buying sex. Risky alcohol consumption was common, with 23% engaging in possible hazardous use according to the WHO Alcohol Use Disorders Identification Test.²⁸

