- Autonomous NGO "Scientific and Educational Center "Most v budushee" (Bridge to the future) IRB#1 (00010190) in Russia

(2) Referral for medical or psychological treatment as the result of study participation if needed: The project team works closely with the Tajik Union in Moscow as an NGO that advocates and represents the interests of Tajiks in the Russian diaspora including their legal problems related to drug use or other illegal activities. The Union will arrange referral of services for participants who (if any) experience legal problems related to drug use or undue psychological stress due to their participation in the study. Participants who report recent thoughts of self-harm or suicidal ideation during an interview will be referred to the Union for assistance in accessing mental health services.

(3) HIV/HCV rapid testing will be voluntary and sharing results with the research will be optional.

Participants who receive a positive confirmatory test will be referred to the Tajik Union for assistance in accessing follow-up services in Moscow through the Volunteer Doctors Association or linkage to care in Tajikistan.

(4) Procedures for Research Team Management of AEs, SAEs and Other Study Risks: All research staff and session facilitators will be trained in how to recognize and appropriately respond to both an adverse event (AE) and a serious adverse event (SAE) should one should occur as part of the study. Staff members will be instructed that such events or incidents must be reported immediately to the Moscow site coordinator and documented using a specially prepared project form, and then reported within 24 hours to Drs. [name] and [name]. They, in turn, will inform the NIH funding agency and also the IRBs of the University of Illinois at Chicago (FWA00000083), PRIZMA Research Center (FWA00017140), and the Scientific and Educational Center in Moscow (IRB #00010190). Further action will be taken under the advisory guidance of the three IRBs and NIH. (See also below for further details on actions to be taken with a possible breach of confidentiality.)

(5) At subway stops where on-duty Moscow police are known to stop and check the documents of passengers with non-Slavic (Russian) appearance, group facilitators will accompany intervention participants to and from the station to the PRIZMA office for the group sessions.

(6) Strategies to protect privacy and confidentiality:

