9.2 SAMPLE SIZE DETERMINATION

We estimated power allowing up to 10% attrition among intervention participants and up to 15% attrition among network members. Power calculations were computed using PASS software and considering effects observed in the pilot study.

We expect to see large reductions in syringe sharing and condomless sex in the MASLIHAT intervention group, and little change in these behaviors in the control group. In the pilot study, syringe sharing decreased from 52% at baseline to 0% at six months, and condomless sex decreased from 35% at baseline to 1% at six months. For binary outcomes, we computed Mixed Models Tests for Two Proportions in a 3-Level Hierarchical Design (Level-3 Randomization), with an intracluster correlation of 0.05 and alpha=.01. We computed power for outcomes ranging from 0.30 to 0.50 for the control group, and 0.05 to 0.15 for the MASLIHAT intervention group, and with 10, 20 or 30 subjects per cluster, representing intervention participants, network members, and the complete sample. We will have at least 80% power to detect predicted changes in condomless sex, and over 90% power to detect predicted changes in syringe sharing. In the larger sample, we will have adequate power to detect effects even if they are not as large as anticipated.

The intervention also targets alcohol use and in the pilot study, days of alcohol use in the past month decreased from 5 to 2, with $b/SE = -6.52$, yielding a Cohen's d effect size of -0.69. We estimated power by computing Mixed Models Tests for the Slope Difference in a 3-Level Hierarchical Design with Fixed Slopes (Level-3 Randomization), with subject $icc=0.30$ and $alpha=0.01$, for a standardized mean difference (SMD) of 0.50 to 0.70, with cluster sizes of 10, 20. and 30. For the intervention participants, we will have at least 80% power to detect a $SMD=0.70$; for network members we will have at least 80% power to detect a $SMD=0.50$, and for the complete sample we will have at least 80% power to detect a $SMD=0.41$.

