For HIV and hepatitis C virus (HCV) outcomes, we computed detectable effects for a one-sided Test for the Difference between Two Poisson Rates in a Cluster-Randomized Design, given our sample with $k=30$ subjects per cluster, coefficient of variation (CV) = 0.50 for the control group and CV=1 for the intervention group, $alpha=0.05$, and $power=0.80$. Assuming a base rate HIV incidence of 10% for the control group, we will have at least 80% power to detect an event rate ratio of 0.11, corresponding to an incidence rate of 1% in the treatment group. For HCV, we must assume that a fair number of the sample will be infected as baseline and therefore excluded from the analysis. Assuming 15 subjects per cluster and HCV base rate incidence of 40%, we will have at least 80% power to detect an event rate ratio of 0.21, corresponding to an incidence rate of 8.6% in the treatment group.

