9.4.3 ANALYSIS OF THE SECONDARY ENDPOINT(S)

Secondary outcomes are HIV and HCV incidence over 12 months. Participants who are HIV antibody positive at baseline will be excluded from the analysis. Participants who are HCV RNA positive at baseline and at 6-months (i.e. chronic infection) will be excluded from the analysis. HCV infection will be operationalized as a positive antibody test following a negative antibody test, or for persons who are AB+ at baseline, a positive HCV RNA test following a negative HCV RNA test. We will conduct a missing data analysis to check for differences between participants with and without test results. If more than 5% of the data are missing we will employ full-information maximum likelihood methods using Mplus.

We will compare incidence rates of HIV and HCV infection between the two intervention conditions among intervention participants, and among network members, with GEE modified Poisson regression to estimate relative risks, adjusted for clustering by recruitment site.⁷⁵ We will estimate the effect of intervention condition, adjusting for covariates including age, education, duration of injection, and length of time in Russia if they are related to the outcome at baseline or if they vary significantly across conditions. The results will be reported as relative risk ratios with 95% confidence intervals, and exact p-values.

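### The HIV power statement in Section 9.2 makes no deduction for men HIV-positive at baseline, whom Section 9.4.3 excludes; the shortfall is modest and depends on a prevalence the documents do not give

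*Combined protocol and SAP*

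**What the plan says.** Section 9.2 bases the HIV calculation on a "one-sided Test for the Difference between Two Poisson Rates in a Cluster-Randomized Design" with alpha 0.05, power 0.80, 30 subjects per cluster, coefficients of variation of 0.50 (control) and 1 (intervention), and a control incidence of 10%. It concludes that "we will have at least 80% power to detect an event rate ratio of 0.11", which it equates to about 1% incidence in the intervention arm.

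The same section explains where 30 comes from. Cluster sizes of 10, 20 and 30 stand for index participants, network members and everyone together, and "We estimated power allowing up to 10% attrition among intervention participants and up to 15% attrition among network members".

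For the other virus the section goes a step further: "For HCV, we must assume that a fair number of the sample will be infected as baseline and therefore excluded from the analysis". It then uses 15 per cluster, a 40% control incidence and a detectable ratio of 0.21 (8.6%).

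Section 9.4.3 sets the HIV analysis set: "Participants who are HIV antibody positive at baseline will be excluded from the analysis". It compares incidence among index participants and, separately, among network members. Section 5.1 has no criterion on HIV status, and Section 8.1 does not require testing for enrolment. Section 2.3.3 adds that "HIV/HCV rapid testing will be voluntary and sharing results with the research will be optional".

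The only HIV prevalence figures for people who inject are in Section 2.2 (item 1.2): "HIV prevalence among PWID in Tajikistan is estimated at 13.5% compared to 25.6% in the Russian Federation".

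**The concern.** The HIV incidence analysis can use only men who are negative at baseline. The planning figure counts every man expected to remain after attrition. Because HIV-positive men may enrol and are removed later, the number at risk per site must be below 30 unless baseline prevalence is zero, and no section assumes that. The HCV calculation in the same paragraph shows that the authors had this mechanism in view.

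The statement claims at least 80% power with almost no slack, so a small deduction breaks it. If it stands, a null HIV result would be judged against power that the analysed men do not provide.

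**Working it through.** **Inputs.** 12 sites, 6 per arm (Section 6.3). 140 index participants and 280 network members (Section 5.5). Attrition of 10% and 15%, one-sided alpha 0.05, control rate r0 = 0.10, CV0 = 0.5, CV1 = 1 (Section 9.2). At ratio 0.11, r1 = 0.011.

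**Men per site.** Enrolled: 420/12 = 35. After attrition: index 126/12 = 10.5, network 238/12 = 19.8, together 30.3. Attrition alone accounts for the step from 35 to 30.

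**Formula (inferred).** With k men per site and K sites per arm:

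V = (r0 + r1)/k + CV0²·r0² + CV1²·r1²

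power = Φ( √(K − 1) · (r0 − r1)/√V − 1.645 )

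The K − 1 is the usual one-cluster correction for few clusters.

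**Reproducing the plan.**
- HIV, k = 30: V = 0.111/30 + 0.0025 + 0.000121 = 0.006321. Then √5 × 0.089/√0.006321 − 1.645 = 0.858, so power is 80.5%. Solving for 80% power gives a ratio of 0.114.
- HCV, k = 15, r0 = 0.40, r1 = 0.086: power 80.0%; solving gives 0.215, a rate of 8.6%.

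Both agree with the stated 0.11 and 0.21. Variants that miss at least one of them:
- one-sided without the correction: 0.170 and 0.262
- two-sided with it: 0.033 and 0.148
- two-sided without it: 0.096 and 0.200

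**Break-even.** Power at ratio 0.11 equals 80% at k = 29.3. That is a baseline prevalence of 1 − 29.3/30 = about 2%, or about 3% from the unrounded 30.3.

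**After removing men positive at baseline.** k = 30 × (1 − prevalence). All prevalences are assumptions; the last two are the Section 2.2 figures used as proxies.

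| Assumed prevalence | k | Power at ratio 0.11 | Ratio detectable at 80% |
|---|---|---|---|
| 0 | 30.0 | 80.5% | 0.114 |
| 5% | 28.5 | 79.4% | 0.105 |
| 10% | 27.0 | 78.2% | 0.094 |
| 13.5% | 26.0 | 77.4% | 0.086 |
| 25.6% | 22.3 | 73.9% | 0.053 |

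Starting from 30.3 instead of 30 changes the last two powers to 77.6% and 74.1%.

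**The comparisons that Section 9.4.3 names.** Same formula, one-sided, ratio 0.11, assumed prevalence 13.5% to 25.6%:
- Network members: k = 19.8 × 0.865 = 17.2 to 19.8 × 0.744 = 14.8; power 67% to 63%.
- Index participants: k = 10.5 × 0.865 = 9.1 to 10.5 × 0.744 = 7.8; power 50% to 46%.

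**The case against.** **The formula is inferred.** Section 9.2 names software and a test but prints no equation. Without the one-cluster correction, power is 83.6% at 13.5% prevalence and 80.4% at 25.6%. A simulated t-test on site-level rates gave about 87% at 26 per site and 83% at 22. These methods also put power at 30 per site at 86.4% and about 90%, so they are not the plan's calculation and do not rescue its figure. What stands is that the shortfall is shown for the plan's approximation, not for the GEE modified Poisson model of Section 9.4.3.

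**Retention may be better than allowed for.** The pilot (Section 2.2, item 1.11(b)) lost no peer educators and 5% of network members. That would leave (140 + 280 × 0.95)/12 = 33.8 per site. Removing 13.5% gives 29.3 and power of 80.0%; removing 25.6% gives 25.2 and 76.7%. But Section 9.2 makes its claim under the 10% and 15% allowance, and the pilot ran only 6 months, whereas the HIV outcome needs a 12-month test.

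**Thirty might already be net of positives.** 35 × 0.865 = 30.3 as well. On that reading attrition would be uncounted, and Section 9.2 says it was allowed for.

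**Little changes in practice.** The secondary endpoint is a 50% reduction. At ratio 0.5 the same formula gives 30% power with 30 per site and 29% to 27% after the deduction. The plan already claims to detect only an 89% reduction. This stands, and it limits the weight of the point.

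**Prevalence.** A reader might take 13.5–25.6% as the prevalence in the trial population, and 22–26 men per site as fact. Section 2.2 gives those figures for people who inject in Tajikistan and in Russia. It also reports that only 9 of 106 surveyed migrants injected with a non-Tajik and that diagnosed migrants face deportation, both reasons to doubt the Russian figure as a proxy.

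**Conclusion.** The omission is real. The HIV figure counts men whom the analysis rule removes, while the HCV figure beside it does not. The printed ratio reproduces from its inputs, so this is a missing assumption, not a slip in calculation.

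Under the formula that matches both stated ratios, and under the plan's own attrition allowance, baseline prevalence above about 2–3% takes power below 80%. The loss is modest: about 1 point at 5% prevalence, and 3 to 7 points over the assumed 13.5–25.6%.

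Two stronger inferences are not supported. One is a specific further loss from voluntary testing. Uptake below 100% would lower k, but the documents give no rate, and a rate that included men lost before month 12 would count attrition twice. The other is that 74–77% is the right figure for the planned analysis. It is pooled and one-sided, whereas Section 9.4.3 compares the two participant types separately and the general approach in Section 9.4.1 specifies two-tailed tests.

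**What to change.** In Section 9.2, compute the HIV figure on men HIV-negative at baseline, as is done for HCV. State the assumed baseline prevalence and testing uptake, label both as assumptions, and show a range. Restate the power at ratio 0.11 or the ratio detectable at 80%. Label any pooled, one-sided figure as such, and beside it give the power for index participants and for network members separately, since those are the comparisons in Section 9.4.3. Name the formula or software procedure so that the figure can be checked. The formal SAP announced in Section 9.1 should carry the same numbers.

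The cost is a rewrite of one paragraph and a less favourable stated figure. Enrolment, design and procedures do not change.

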2.2 BACKGROUND

1.1. The role of labor migration in HIV acquisition and transmission is a high-priority issue for both developing and developed countries.^{4, 10} Central Asia is the world's second largest migration pipeline,

and reports the fastest growing rates of HIV/AIDS globally.^{11, 12} Tajikistan, a small impoverished country in Central Asia, is one of the most remittance dependent countries in the world.^{13, 14} After a 2-year decline due to the economic downturn in Russia,¹⁵ remittances are now rising again. Remittance inflow to Tajikistan through migrant labor in Russia accounted for an estimated \$2.2 billion per year or 31% of its GDP in 2017.¹³ It is estimated that almost one million Tajik citizens work outside the country; most of these migrants are men, and that one-third of men age 20 to 39 have left Tajikistan at least once in their lives to find temporary work.¹⁴ Most of these migrant workers find employment in the Russian Federation, mainly working in construction, trade, agriculture, and maintenance.^{16, 17} Most stay in Russia for 2-3 years due to the transportation costs in getting there plus legal restrictions that make it difficult to obtain visa papers that allow annual or frequent crossings. A World Bank study found that over a 2.5 year period (May 2015-December 2017), 26% of the households surveyed had a migrant worker at some time.¹⁸ According to the Ministry of Health of Tajikistan, migrants make up 14.9% of the total number of HIV infected men and women, and 87% of HIV-infected are men.

As often true for labor migrants, life in Russia for Tajik male workers is hard. Previous research reveals that Tajik migrants perform Russia's most dangerous construction work and low-wage jobs.¹⁹ They often are the focus of Russian hostility and violence including physical beatings, and they reside in substandard living conditions, eat non-nutritious meals during brief work breaks, and have little or no access to Russian health care if sick or injured.²⁰ Also, some unknown number, having entered Russia illegally, constantly hides from authorities. Moreover, if diagnosed with HIV they face deportation and restriction from re-entry.²¹ These factors, along with the psychosocial stress and separation from family and friends, can coalesce to produce emotional distress including depression and feelings of loneliness that encourage risky behavior.²²

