5.5 STRATEGIES FOR RECRUITMENT AND RETENTION

The study will enroll a total of 420 male Tajik migrant MWID including 140 index participants (MASLIHAT or control intervention) and 280 IDU network members. Based on pilot study experience, since recruitment materials will specify the requirements for participation, nearly all men who present for screening will meet the criteria for enrollment. We anticipate screening up to 150 MWID for participation as index participants, and up to 300 MWID for participation as network members.

Timing for recruitment. Recruitment of index participants (70 MASLIHAT peer educators and 70 control group participants) will take place throughout the intervention/baseline data collection period (18 months) through referrals from the Tajik diaspora organizations and recruitment at the 6 worksites and 4 bazaar sites until sample requirements for 140 index participants are met. Network member recruitment (n=280) will occur through referral by the index participants. As with the pilot study, only

index participants who successfully recruit two eligible network members will participate in the interventions. Recruitment will be conducted intensively at two sites at a time, one assigned to the intervention and the other to the control. We will recruit from these sites until we have filled two groups of 5 to 7 eligible participants (each having successfully recruited 2 network members). Groups will be closed to new members after the first session. When we have filled 2 groups for each site in the pair, the recruitment team will move on to the next pair of sites. We will run four intervention groups each quarter (2 MASLIHAT and 2 TANSIHAT) over a period of 18 months (20 groups total).

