6.3 MEASURES TO MINIMIZE BIAS: RANDOMIZATION AND BLINDING

The 12 recruitment sites will be pair matched and randomly assigned to a study arm. One of each pair will be assigned to MASLIHAT and the other to the control condition. [name] will create the matched pairs based on site characteristics, and randomization will be determined by the PI using a random number generator. A random number will be generated for each site, and within each matched pair, the site with the smaller number will be assigned to MASLIHAT. To minimize bias during recruitment, site assignments will be masked from project staff engaged in recruitment. The PI will inform the Moscow project coordinator of the site assignment as needed for group scheduling, after the first cohort of participants has been filled for the site. Participants will be informed of their assignment at the time of scheduling the group sessions. [name] will also have access to this information as needed, after recruitment activities are underway. Interviewers will be blinded to site assignment, and the same interview instrument will be used for MASLIHAT and control condition participants. Session facilitators, who may become aware of the recruitment sites from which participants originated, will be instructed during training not to reveal this information to interviewers. Intentional or unintentional breaking of the blind is to be reported to the PI.

The randomization codes will be kept in a password-protected file accessible to the PI, co-investigators, the project coordinator, and the data manager. When preparing data for analysis, the data manager will

blind code recruitment site and study arm. Masking will be removed for reporting interim results to the DSMB.

In addition, we will adopt a position of clinical equipoise. Intervention facilitators and interviewers will be informed that we are testing two different interventions, but neither is assumed to be superior to the other. Facilitators will be assigned to one or the other, while interviewers will be blinded to participant condition. Data collection will be conducted by interviewers who are not involved in intervention delivery. Interviews will be standardized using a computer-assisted instrument, and sensitive sections will be self-administered.

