Peer educator personal development. Measures of peer educator personal development (in addition to knowledge and behavior change) will be administered at baseline and at 12-month follow-up, including self-esteem, self-efficacy, and substance use self-stigma. The 10 items of the Rosenberg Self-Esteem Scale^{70, 71} assess a person's overall evaluation of his or her worthiness as a human being, including subscales of self-competence and self-liking. Items are rated on a 4-point scale from 1 (strongly disagree) to 4 (strongly agree). The New General Self-Efficacy Scale⁷² includes 8 items to measure general self-efficacy (e.g. "I will be able to achieve most of the goals that I set for myself.") rated on a Likert scale from strongly disagree to strongly agree. Internalized stigma of substance use will be assessed with 6 items adapted from a measure of HIV stigma⁷³, rated on a 5-point Likert-type scale, e.g. "I feel ashamed of being a person who uses drugs".

Intervention engagement

Session facilitators will record participant attendance, note homework completion, and rate participant engagement at each session.

HIV/HCV counseling and testing.

Intervention participants and network members will be referred to the Moscow HIV Prevention Center (MHPC) for voluntary HIV/HCV rapid and confirmatory testing and counseling following the baseline interview, and later at the 6-month (HCV) and 12-month (HIV and HCV) follow-up. We chose to not require HIV testing as a condition of study enrollment as its impact on study recruitment and participation are unknown. Participants will be informed that their results will be shared with the research study unless they choose to opt out. We will explain the measures we will employ to maintain the confidentiality of the results.

We will give each participant a card with a code number on which test results will be reported. The testing code number will be separate from the research ID number used to identify interviews, and will

consist of a group number and an individual code. The list matching testing codes with research IDs will be kept in a secure REDCap database separate from locator data and interview data. Participants who object to having their test results linked to their personal interview data will be given the option of blacking out the individual code number, keeping only the group number. This will allow us to track results by intervention group even if the results cannot be linked to individuals.

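### The HIV power in section 9.2 counts every man retained after attrition, with no deduction for men HIV positive at baseline or without linked test results; the HCV figure may carry the same gap

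*Combined protocol and SAP*

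**What the plan says.** Section 9.2 bases the infection endpoints on a "one-sided Test for the Difference between Two Poisson Rates in a Cluster-Randomized Design", with alpha 0.05, power 0.80, and coefficients of variation of 0.50 (control) and 1 (intervention). For HIV it takes 30 men per site and 10% control incidence, and reports a detectable ratio of 0.11. For HCV it says that a fair number will already be infected and continues: "Assuming 15 subjects per cluster and HCV base rate incidence of 40%, we will have at least 80% power", for a ratio of 0.21 (8.6% in the intervention arm). The only other loss in 9.2 is attrition of up to 10% (index participants) and 15% (network members).

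Section 9.4.3 excludes men who are HIV antibody positive at baseline. It defines HCV infection by a negative result followed by a positive one.

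On testing, section 8.1 says: "We chose to not require HIV testing as a condition of study enrollment as its impact on study recruitment and participation are unknown". It adds: "Participants will be informed that their results will be shared with the research study unless they choose to opt out". Men are referred to a separate testing centre, and may black out the individual code so that only a group number remains. Section 2.3.3 calls testing voluntary and sharing optional. Section 2.2 says of migrants that "if diagnosed with HIV they face deportation and restriction from re-entry".

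**The concern.** The power calculation needs the number of men in whom a new infection could be observed. For HIV, that means a man who tests negative at baseline, tests again at 12 months, and lets both results be linked to him. The number used in 9.2 is instead the number expected to remain in follow-up. Neither infection at baseline nor missing results has been deducted, although 9.4.3 makes the first an exclusion and sections 8.1 and 2.3.3 create several routes to the second.

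For HCV a deduction is made, but only baseline infection is given as the reason.

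At stake is how far the HIV and HCV comparisons can be relied on. A reader who takes 80% at face value would give a null result more weight than the design supports.

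**Working it through.** **Where 30 comes from.** Section 5.5 plans 420 men, "including 140 index participants (MASLIHAT or control intervention) and 280 IDU network members". Section 6.3 says: "The 12 recruitment sites will be pair matched and randomly assigned to a study arm". That is 420/12 = 35 per site. After attrition, 140 × 0.90 + 280 × 0.85 = 126 + 238 = 364 remain, and 364/12 = 30.3 per site. This is the 30 used for HIV, so every retained man is counted.

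**Reproducing the plan.** The Hayes-Bennett formula for cluster-randomised rates, solved for power with c = 6 sites per arm and one-sided alpha 0.05:

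V = (λ0 + λ1)/k + CV0²λ0² + CV1²λ1²

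power = Φ( √[(c − 1)(λ0 − λ1)²/V] − 1.645 )

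- HIV, λ0 = 0.10, λ1 = 0.011, k = 30: V = 0.0037 + 0.0025 + 0.000121 = 0.006321. √(5 × 0.007921/0.006321) = 2.503. Power = Φ(0.858) = 80.5%. The ratio detectable with 80% power is 0.114.
- HCV, λ0 = 0.40, λ1 = 0.086, k = 15: V = 0.0324 + 0.0400 + 0.007396 = 0.079796. √(5 × 0.098596/0.079796) = 2.486. Power = Φ(0.841) = 80.0%. The detectable ratio is 0.215.

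Both match the printed 0.11 and 0.21 (8.6%). Taking HIV incidence as exactly the printed 1%, rather than 1.1%, gives 81.5%.

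**Margin for HIV.** Eighty per cent power at ratio 0.11 needs V = 5 × 0.007921/(1.645 + 0.842)² = 0.006406. So k = 0.111/(0.006406 − 0.002621) = 29.3. A loss of about one man per site uses up the margin.

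**Reducing k.** Multiply k by the share with linked results at both ends (joint uptake). For HIV, also multiply by one minus baseline prevalence. Section 2.2 gives prevalence among people who inject drugs as 13.5% (Tajikistan) and 25.6% (Russia). Neither was measured in this study population. Uptake is assumed throughout. The HCV column assumes that 15 contains no allowance for non-testing.

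| Joint uptake | HIV, none removed | HIV, 13.5% removed | HIV, 25.6% removed | HCV from 15 |
|---|---|---|---|---|
| 100% | 80.5% | 77.4% | 73.9% | 80.0% |
| 90% | 78.2% | 74.9% | 71.2% | 78.4% |
| 80% | 75.6% | 72.1% | 68.2% | 76.5% |
| 65% | 70.5% | 66.6% | 62.5% | 72.8% |
| 50% | 63.4% | 59.4% | 55.2% | 67.4% |

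From uptake alone, the HIV ratio detectable with 80% power moves from 0.114 to 0.094 (90%) and 0.069 (80%). At 50% no ratio reaches 80% power, even with no infections in the intervention arm. With full testing and 13.5% or 25.6% removed it is 0.086 or 0.053. For HCV it moves from 0.215 to 0.203 (90%), 0.188 (80%) and 0.114 (50%).

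**HIV and HCV are not alike.** HIV is tested twice (baseline, 12 months), HCV three times (baseline, 6 and 12 months). Suppose each round is attended independently by 80% or 70% of men. HIV joint uptake is 0.8² = 64% or 0.7² = 49%. For HCV, a baseline plus at least one later result is available for 0.8 × (1 − 0.2²) = 77% or 0.7 × (1 − 0.3²) = 64%, giving power of about 76% or 72%. A man with only a 6-month result contributes less follow-up, so these HCV figures are slightly generous.

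**Slack in the HCV 15.** Section 2.2 puts HCV prevalence at 23% to 67%. Of 30.3 retained men per site, 23.4 would be uninfected at 23%, so 15 would correspond to 15/23.4 = 64% uptake. At 50%, 15.2 remain and there is no slack. At 67%, 10.0 remain, and power is 73% with full testing.

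**The case against.** The strongest reply is that the size of the uptake loss is not in the documents. Nothing there says that half or a fifth of men will go untested, and at 90% joint uptake the loss is only about 2 points. Men who test once may be likelier to test again. Code numbers kept apart from the research ID, and follow-up of missing results, should also help. A reader might infer that power will fall to 63-76%. That is the HIV range at an assumed 50% to 80% uptake, and the documents do not support it as a forecast. Nor does it apply to HCV.

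A reader might also infer that the HCV calculation certainly assumes full testing. Section 9.2 does not say so. At the low end of the prevalence range, 15 already leaves room for much non-testing, and antibody-positive, RNA-negative men can remain at risk under 9.4.3.

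The attrition allowance may itself be cautious. The pilot lost no peer educators and 5% of network members, over six months. At that retention there would be (140 + 266)/12 = 33.8 men per site, so 30 would correspond to about 89% uptake for HIV. This could offset one of the two missing deductions, at the lower prevalence, but not both. It is also not the allowance that 9.2 claims.

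Section 9.4.3 does plan a missing-data analysis and full-information maximum likelihood. That may limit bias, but it does not recover unobserved infections. Results carrying only a group number can be counted by group, but a man's later result cannot be tied to his baseline one.

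Other limits on this analysis are separate matters: 9.4.3 compares index participants and network members separately, 9.4.1 specifies two-tailed tests, and power for the stated 50% reduction is only about 30% (HIV) and 36% (HCV) by the same formula. They do not rescue the stated 80%.

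**Conclusion.** The point holds for HIV. The 30 per site is every retained man, while the planned analysis can use only those negative at baseline with linked results at both ends. The baseline exclusion alone takes 80.5% to about 77-74% if the prevalences in section 2.2 apply, and needs no assumption about uptake. With an assumed 80% joint uptake as well, power is about 72-68%.

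For HCV it holds conditionally. If 15 excludes only men infected at baseline, power is about 78% at 90% usable results, 76-77% at 80% and 72-73% at 64%. If baseline prevalence is near 23%, there may be no shortfall. The defect is that 9.2 does not say what 15 contains.

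These are secondary endpoints. Nothing here shows that more men must be enrolled, and the calculation does not touch the primary behavioural outcomes.

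**What to change.** In 9.2:

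- Define the per-site number for each virus as men at risk at baseline with linked baseline and follow-up results.
- State the assumed baseline prevalence and joint test uptake for HIV and for HCV, and say whether the 15 for HCV includes any allowance for non-testing.
- Replace the single HIV and HCV figures with a table of power and detectable ratios at, for example, 90%, 80%, 65% and 50% joint uptake, with the HIV rows also net of baseline positives.

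The cost is some wording and one table, with no change in enrolment or procedures. The downside is that the stated power and detectable effects for the secondary endpoints become less favourable.
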